**11.9 Reporting Table for Late Phase 2 and Phase 3 Studies – Table A**

Expedited Reporting Requirements for Adverse Events that Occur on Studies under an IND/IDE within 30 Days of the Last Administration of the Investigational Agent/Intervention 

FDA REPORTING REQUIREMENTS FOR SERIOUS ADVERSE EVENTS (21 CFR Part 312)  NOTE: Investigators MUST immediately report to the sponsor (COG) ANY Serious Adverse Events, whether or not they are considered related to the investigational agent(s)/intervention (21 CFR 312.64)  An adverse event is considered serious if it results in ANY of the following outcomes:  1) Death.  2) A life-threatening adverse event.  3) Any AE that results in inpatient hospitalization or prolongation of existing hospitalization for <math>\geq 24</math> hours. This does not include hospitalizations that are part of routine medical practice.  4) A persistent or significant incapacity or substantial disruption of the ability to conduct normal life functions.  5) A congenital anomaly/birth defect.  6) Important Medical Events (IME) that may not result in death, be life threatening, or require hospitalization may be considered serious when, based upon medical judgment, they may jeopardize the patient or subject and may require medical or surgical intervention to prevent one of the outcomes listed in this definition. (FDA, 21 CFR 312.32; ICH E2A and ICH E6.)
				

ALL SERIOUS adverse events that meet the above criteria MUST be immediately reported to the NCI via CTEP-AERS within the timeframes detailed in the table below.
				
Hospitalization	Grade 1 Timeframes	Grade 2 Timeframes	Grade 3 Timeframes	Grade 4 & 5 Timeframes
Resulting in Hospitalization <math>\geq 24</math> hrs	7 Calendar Days			24-Hour Notification 5 Calendar Days
Not resulting in Hospitalization <math>\geq 24</math> hrs	Not Required		7 Calendar Days	

NOTE: Protocol specific exceptions to expedited reporting of serious adverse events are found in the Specific Protocol Exceptions to Expedited Reporting (SPEER) portion of the CAEPR. Additional Special Situations as Exceptions to Expedited Reporting are listed below.  Expedited AE reporting timelines are defined as:  “24-Hour; 5 Calendar Days” – The AE must initially be reported via CTEP-AERS within 24 hours of learning of the AE, followed by a complete expedited report within 5 calendar days of the initial 24-hour notification.  “7 Calendar Days” – A complete expedited report on the AE must be submitted within 7 calendar days of learning of the AE.
				

SAEs that occur more than 30 days after the last administration of investigational agent/intervention and have an attribution of possible, probable, or definite require reporting as follows:  Expedited 24-hour notification followed by complete report within 5 calendar days for:
 
 
• All Grade 4, and Grade 5 AEs
 
 
Expedited 7 calendar day reports for:
 
 
• Grade 2 adverse events resulting in hospitalization or prolongation of hospitalization
 
• Grade 3 adverse events
 
				

**11.10 Protocol Specific Additional Instructions and Reporting Exceptions**

- **Grades 1-4 myelosuppression (anemia, neutropenia, thrombocytopenia) do not require expedited reporting.**
- **Grades 1-2 AST/ALT elevations do not require expedited reporting.**

**11.11 Reporting of Adverse Events for commercial agents – CTEP-AERS abbreviated pathway**

The following are expedited reporting requirements for adverse events experienced by patients on study who have not received any doses of an investigational agent on this study. Commercial reporting requirements are provided in Table B.

COG requires the CTEP-AERS report to be submitted **within 7 calendar days** of learning of the event.

**Table B**

**Reporting requirements for adverse events experienced by patients on study who have NOT received any doses of an investigational agent on this study.**

**CTEP-AERS Reporting Requirements for Adverse Events That Occur During Therapy With a Commercial Agent or Within 30 Days**

Attribution	Grade 4		Grade 5
	Unexpected	Expected	
Unrelated or Unlikely			CTEP-AERS
Possible, Probable, Definite	CTEP-AERS		CTEP-AERS

This includes all deaths within 30 days of the last dose of treatment with a commercial agent, regardless of attribution. Any death that occurs more than 30 days after the last dose of treatment with a commercial agent that can be attributed (possibly, probably, or definitely) to the agent and is not due to cancer recurrence must be reported via CTEP-AERS.

**11.12 Routine Reporting of Adverse Events**

**Note:** The guidelines below are for routine reporting of study specific adverse events on the COG case report forms and do not affect the requirements for CTEP-AERS reporting.

Routine reporting is accomplished via the Adverse Event (AE) Case Report Form (CRF) within the study database. For this study, routine reporting will include all CTEP-AERS reportable events and Grade 3 and higher Adverse Events.

## 12.0 STUDY REPORTING AND MONITORING

The Case Report Forms and the submission schedule are posted on the COG website with each protocol under “Data Collection/Specimens”. A submission schedule is included.

### 12.1 CDUS

This study will be monitored by the Clinical Data Update System (CDUS). Cumulative CDUS data will be submitted quarterly to CTEP by electronic means. Reports are due January 31, April 30, July 31 and October 31. This is not a responsibility of institutions participating in this trial.

### 12.2 Data and Safety Monitoring Committee

To protect the interests of patients and the scientific integrity for all clinical trial research by the Children’s Oncology Group, the COG Data and Safety Monitoring Committee (DSMC) reviews reports of interim analyses of study toxicity and outcomes prepared by the study statistician, in conjunction with the study chair’s report. The DSMC may recommend the study be modified or terminated based on these analyses.

Toxicity monitoring is also the responsibility of the study committee and any unexpected frequency of serious events on the trial are to be brought to the attention of the DSMC. The study statistician is responsible for the monitoring of the interim results and is expected to request DSMC review of any protocol issues s/he feels require special review. Any COG member may bring specific study concerns to the attention of the DSMC.

The DSMC approves major study modifications proposed by the study committee prior to implementation (e.g., termination, dropping an arm based on toxicity results or other trials reported, increasing target sample size, etc.). The DSMC determines whether and to whom outcome results may be released prior to the release of study results at the time specified in the protocol document.

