### 9.3 Study Design

This trial is a multi-strata Phase 2 study of IMG901. The primary endpoint will be objective response by RECIST criteria. As of Amendment #1, each stratum will accrue a maximum of 16 evaluable patients. IMG901 will be identified as having sufficient activity for further study in a particular stratum if there are at least 4 responses (PR or CR) confirmed by central review. This design will be used for all strata which have not been closed prior to the activation of Amendment #1.

We will consider the agent not of sufficient interest for further evaluation in a disease category if the true response rate is 15%. ( $H_0$  is a true response rate of 15%.)  $H_a$  is a true response rate of 40%. Each stratum will accrue 16 evaluable patients. Thus, there will be a maximum of 96 evaluable patients. If the agent has a true response rate of 15%, the rule described herein will identify the agent of sufficient activity for further study with probability 0.079 (Type I error). If the agent has a true response rate of 40%, the rule described herein will identify the agent of sufficient activity for further study with probability 0.833 (power against the alternative hypothesis  $p = 0.40$ ). In addition to making the decision to accept or reject the drug, the final results will be reported after all patients have been identified as having a CR, PR, or PD as their response according to protocol-specified criteria.

Prior to Amendment #1, the trial used a Simon two-stage optimal design in each stratum. The best response of disease was examined separately in each stratum. Within each stratum, the following two-stage design for 15% response rate vs. 40% response rate with  $\alpha = \beta = 0.10$  was employed:

	Cumulative Number of Responses at the End of the Stage	Decision
Stage 1: Enter 10 evaluable patients	0 or 1 2 or more	Terminate the trial for this stratum because the agent is ineffective. Proceed to Stage 2.
Stage 2: Enter 12 additional evaluable patients	5 or fewer 6 or more	Terminate the trial for this stratum because the agent is ineffective. Terminate the trial for this stratum because the agent is effective.

A comparison of the operating characteristics of the single stage and two-stage designs

appears below.

True response rate	Simon's optimal design (10 + 12 [2,6])			Single- stage design (16[4])

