	Probability of stopping early for lack of activity	Probability of identifying agent as effective	Expected number of patients accrued	Probability of identifying agent as effective
5%	0.914	0.001	11.03	0.001
10%	0.736	0.016	13.17	0.017
15%	0.544	0.091	15.47	0.079
20%	0.376	0.246	17.49	0.202
25%	0.244	0.451	19.07	0.370
30%	0.149	0.650	20.21	0.550
35%	0.086	0.804	20.97	0.711
40%	0.046	0.903	21.44	0.833
45%	0.023	0.957	21.72	0.915
50%	0.011	0.983	21.87	0.962

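### Since Amendment #1 no prespecified outcome rule closes a stratum, so by default enrolment can continue after the required number of responses is out of reach

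*Combined protocol and SAP*

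**What the plan says.** Section 9.3 gives the current design: "As of Amendment #1, each stratum will accrue a maximum of 16 evaluable patients". It then repeats without qualification: "Each stratum will accrue 16 evaluable patients". A stratum succeeds "if there are at least 4 responses (PR or CR) confirmed by central review". The design covers every stratum still open when the amendment took effect.

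The same section describes what was replaced: a Simon two-stage design that closed a stratum at 0 or 1 response in the first 10 patients. The comparison table has a column headed "Probability of stopping early for lack of activity" for the old design only. The single-stage design has no equivalent.

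Elsewhere, section 2.5 makes continued accrual depend on toxicity alone. Section 9.2 sets numerical limits for dose-limiting toxicity and peripheral neuropathy. Section 9.1.1 ends study enrolment once the three primary groups have been evaluated, unless committee leadership extends the secondary strata. That is not a response rule.

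Section 12.2 says the DSMC "reviews reports of interim analyses of study toxicity and outcomes prepared by the study statistician", lets it recommend changing or ending the study, and makes the statistician responsible for watching interim results. It states no outcome threshold and no timing for an outcome look.

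**The concern.** Toxicity has numerical limits and activity has none. Once enough patients in a stratum have failed to respond, the remaining places cannot turn a negative result into a positive one. Patients enrolled after that point still face the neuropathy risk described in sections 2.3.1 and 9.2, and they cannot alter the go/no-go decision for their tumour type. Nothing written tells the statistician or the DSMC when that point has been reached, so the default is to continue to 16. At stake are a few children per trial, not the validity of the result.

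**Working it through.** **Inputs.** From 9.3: n = 16 evaluable per stratum, required responses r, null rate 15%, alternative 40%. From 9.1.1: accrual of 18, 14 and 9 per year for Wilms tumour, rhabdomyosarcoma and neuroblastoma. From 4.1.3 and 9.5: first imaging after cycle 2, then every other cycle, with best response judged over six 21-day cycles (18 weeks).

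**Step 1. The plan's own figures.** The exact binomial P(X ≥ r | 16, p) gives:

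| Rule | p = 0.15 | p = 0.40 |
|---|---|---|
| r = 4 (text) | 0.210 | 0.935 |
| r = 5 | 0.079 | 0.833 |

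The printed 0.079 and 0.833, and all ten rows of the single-stage column, belong to r = 5. The text says 4. Both values are carried below. The old two-stage figures checked do reproduce (at 15%: early stop 0.544, success 0.091, expected N 15.47).

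**Step 2. When success becomes impossible.** With x evaluable non-responders, at most 16 − x responses remain possible. Success is impossible when 16 − x < r, that is, when x reaches k = 17 − r. So k = 13 for r = 4 and k = 12 for r = 5. At most 3 or 4 evaluable patients per stratum can be enrolled after that point.

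**Step 3. Mean number spared if every outcome were known before the next enrolment.** Let M be the patient at whom the k-th non-responder occurs:

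P(M = m) = C(m − 1, k − 1)(1 − p)^k p^(m − k); mean spared = Σ (16 − m) P(M = m).

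- r = 4, p = 0.05: 3 × 0.5133 + 2 × 0.3337 + 1 × 0.1168 = 2.3
- r = 5, p = 0.05: 4 × 0.5404 + 3 × 0.3242 + 2 × 0.1054 + 1 × 0.0246 = 3.4
- r = 4, p = 0.15: 3 × 0.1209 + 2 × 0.2358 + 1 × 0.2476 = 1.1
- r = 5, p = 0.15: 4 × 0.1422 + 3 × 0.2560 + 2 × 0.2496 + 1 × 0.1747 = 2.0

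At 40% the saving is 0.04 or 0.15. These are upper bounds on the mean.

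**Step 4. Allowing for scan delay.** The 18-week window spans about 6.2 Wilms, 4.8 rhabdomyosarcoma and 3.1 neuroblastoma enrolments (accrual × 18/52.18). Many late patients would thus be enrolled before futility was known. The documents give no distribution for when non-response is established. The assumption used is 60% at 1.5 months, 25% at 3 and 15% at 4.5, with Poisson accrual. Simulated mean number spared at a 5% true rate:

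| | Wilms | Rhabdomyosarcoma | Neuroblastoma | Total |
|---|---|---|---|---|
| r = 4 | 0.31 | 0.52 | 0.95 | 1.8 |
| r = 5 | 0.72 | 1.12 | 1.76 | 3.6 |

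At 15% the totals are about 0.7 (r = 4) and 1.7 (r = 5). Faster ascertainment raises these figures and slower ascertainment lowers them.

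**Step 5. Secondary strata.** No accrual rate is given. At an assumed 3 per year, 16 patients take 16/3 = 5.3 years, while 9.1.1 expects the study to need 2 to 3 years, or 6 to 9 patients per secondary stratum. Such a stratum rarely reaches 12 or 13 non-responders before enrolment ends. The simulated saving is 0.001 to 0.12 per stratum at a 5% rate.

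**Step 6. Error rates.** A stratum closed at k non-responders could not have succeeded, so no success is lost and none is created. Type I error and power are exactly those of the fixed-16 rule.

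**Step 7. Precision.** With no responses, the Clopper-Pearson upper 95% limit is 1 − 0.025^(1/n): 26.5% for 0/12, 24.7% for 0/13, 20.6% for 0/16.

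**The case against.** A fixed sample of 16 is a legitimate choice, and 9.3 discloses the loss of the early stop by printing both designs side by side. Oversight exists: the DSMC sees interim outcomes, the statistician monitors them, 9.5 provides quarterly preliminary activity data, and 9.3 also calls 16 a maximum. Late patients still contribute to the toxicity aims and to the response interval. All of this stands, and it limits the point to a missing written trigger.

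Four stronger readings are tempting, and the documents do not support them.

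- **Children will certainly be enrolled after the result is settled.** Section 12.2 leaves the DSMC free to recommend termination. Continuing is the default, not a certainty.
- **The trial-wide saving is large.** Multiplying the upper bounds by six strata gives 6 × 2.3 = 14 to 6 × 3.4 = 20 children. Even with scan delays, adding three secondary strata that run to 16 gives about 7 to 12. The first assumes instant outcomes, and both assume full secondary strata, which the closure rule in 9.1.1 makes unlikely unless leadership extends them.
- **Closing at impossibility recovers the old design's 11.03 patients at a 5% rate.** It does not, because it does not restore the look at 10. The same table gives the old design 15.47 patients at 15% and 21.44 at 40%.
- **A discretionary DSMC stop would damage the type I error.** A stop at impossibility changes nothing, and an earlier futility stop can only lower type I error, at some cost in power.

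**Conclusion.** The point holds as a minor one. After Amendment #1 no prespecified outcome rule closes a stratum, and section 12.2 supplies no trigger, so enrolment can by default continue after the required number of responses has become unreachable. Across the primary strata this concerns about 1.8 to 3.6 children if the true response rate is 5%, and about 0.7 to 1.7 if it is 15%. The lower figure in each pair is for a threshold of 4 and the higher for 5. The estimates rest on the accrual rates in 9.1.1 and the assumed scan delays. More would be spared only if the secondary strata stay open beyond the 9.1.1 closure. The conflict between 4 and 5 responses in 9.3 is a separate and more serious problem, and it must be settled before any closing count is fixed.

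**What to change.** First reconcile the threshold in 9.3 with its printed error rates. Then add to 9.3 and 12.2, keeping only the count that applies:

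> Enrolment to a stratum closes, with notice to the DSMC, once the number of evaluable patients classified as non-responders under 9.5 and 10.6 makes the required number of responses out of 16 unreachable (13 for a threshold of 4, 12 for a threshold of 5). Patients inevaluable under 9.5, and patients who could still have a confirmed response, are not counted.

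The last sentence is needed. Section 9.5 makes a patient inevaluable, not a non-responder, if other anti-cancer treatment intervenes between a first response and its confirmation. Counting that patient could close a stratum that might still succeed, and the error rates would then no longer be preserved.

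Report a stratum closed this way as negative, with its response rate and exact interval. The cost is wording, a wider interval (for example an upper limit of 26.5% in place of 20.6% when there are no responses and 12 are needed to close), and slightly less toxicity data from that stratum. If the sponsor prefers all 16 for precision, 9.3 should say so.

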### 12.3 CRADA/CTA

***NCI/DCTD Standard Language to Be Incorporated into All Protocols Involving Agent(s) Covered by a Clinical Trials Agreement (CTA), a Cooperative Research and Development Agreement (CRADA) or a Clinical Supply Agreement, hereinafter referred to as Collaborative Agreement:***

The agent(s) supplied by CTEP, DCTD, NCI used in this protocol is/are provided to the NCI under a Collaborative Agreement (CRADA, CTA, CSA) between the Pharmaceutical Company(ies) (hereinafter referred to as “Collaborator(s)”) and the NCI Division of Cancer Treatment and Diagnosis. Therefore, the following obligations/guidelines, in addition to the provisions in the “Intellectual Property Option to Collaborator” ([http://ctep.cancer.gov/industryCollaborations2/intellectual\\_property.htm](http://ctep.cancer.gov/industryCollaborations2/intellectual_property.htm)) contained within the terms of award, apply to the use of the Agent(s) in this study:

1. Agent(s) may not be used for any purpose outside the scope of this protocol, nor can Agent(s) be transferred or licensed to any party not participating in the clinical study. Collaborator(s) data for Agent(s) are confidential and proprietary to Collaborator(s) and shall be maintained as such by the investigators. The protocol documents for studies utilizing Agents contain confidential information and should not be shared or distributed without the

permission of the NCI. If a copy of this protocol is requested by a patient or patient's family member participating on the study, the individual should sign a confidentiality agreement. A suitable model agreement can be downloaded from: <http://ctep.cancer.gov>.

2. For a clinical protocol where there is an investigational Agent used in combination with (an)other Agent(s), each the subject of different Collaborative Agreements, the access to and use of data by each Collaborator shall be as follows (data pertaining to such combination use shall hereinafter be referred to as "Multi-Party Data"):
  - a. NCI will provide all Collaborators with prior written notice regarding the existence and nature of any agreements governing their collaboration with NCI, the design of the proposed combination protocol, and the existence of any obligations that would tend to restrict NCI's participation in the proposed combination protocol.
  - b. Each Collaborator shall agree to permit use of the Multi-Party Data from the clinical trial by any other Collaborator solely to the extent necessary to allow said other Collaborator to develop, obtain regulatory approval or commercialize its own Agent.
  - c. Any Collaborator having the right to use the Multi-Party Data from these trials must agree in writing prior to the commencement of the trials that it will use the Multi-Party Data solely for development, regulatory approval, and commercialization of its own Agent.
3. Clinical Trial Data and Results and Raw Data developed under a Collaborative Agreement will be made available to Collaborator(s), the NCI, and the FDA, as appropriate and unless additional disclosure is required by law or court order as described in the IP Option to Collaborator ([http://ctep.cancer.gov/industryCollaborations2/intellectual\\_property.htm](http://ctep.cancer.gov/industryCollaborations2/intellectual_property.htm)). Additionally, all Clinical Data and Results and Raw Data will be collected, used and disclosed consistent with all applicable federal statutes and regulations for the protection of human subjects, including, if applicable, the *Standards for Privacy of Individually Identifiable Health Information* set forth in 45 C.F.R. Part 164.
4. When a Collaborator wishes to initiate a data request, the request should first be sent to the NCI, who will then notify the appropriate investigators (Group Chair for Cooperative Group studies, or PI for other studies) of Collaborator's wish to contact them.
5. Any data provided to Collaborator(s) for Phase 3 studies must be in accordance with the guidelines and policies of the responsible Data Monitoring Committee (DMC), if there is a DMC for this clinical trial.
6. Any manuscripts reporting the results of this clinical trial must be provided to CTEP by the Group office for Cooperative Group studies or by the principal investigator for non-Cooperative Group studies for immediate delivery to Collaborator(s) for advisory review and comment prior to submission for

**APPENDIX II: Possible Drug Interactions**

*The lists below do not include everything that may interact with chemotherapy. Study Subjects and/or their Parents should be encouraged to talk to their doctors before starting any new medications, using over-the-counter medicines, or herbal supplements and before making a significant change in diet.*

**Dexamethasone**

Drugs that may interact with dexamethasone

 
• Antibiotics               
 
○ Ciprofloxacin, levofloxacin, moxifloxacin, clarithromycin, erythromycin, nafcillin, rifabutin, rifampin, telithromycin
 
 
 
• Antidepressants and antipsychotics               
 
○ Aripiprazole, bupropion, citalopram, clozapine, escitalopram, fluvoxamine, lurasidone, nefazodone, quetiapine
 
 
 
• Antifungals               
 
○ Caspofungin, fluconazole, itraconazole, ketoconazole, posaconazole, voriconazole
 
 
 
• Arthritis medications               
 
○ Leflunomide, tofacitinib
 
 
 
• Anti-rejection medications               
 
○ Cyclosporine, sirolimus, tacrolimus
 
 
 
• Antiretrovirals and antivirals               
 
○ Atazanavir, boceprevir, darunavir, delaviridine, efavirenz, etravirine, fosamprenavir, indinavir, lopinavir, nelfinavir, nevirapine, rilpivirine, ritonavir, saquinavir, Stribild, telaprevir, tipranavir
 
 
 
• Anti-seizure medications               
 
○ Carbamazepine, oxcarbazepine, phenobarbital, phenytoin, primidone
 
 
 
• Heart medications               
 
○ Amiodarone, amlodipine, dronedenarone, verapamil
 
 
 
• Some chemotherapy (be sure to talk to your doctor about this)
 
• Some oral contraceptives or birth control medications
 
• Many other drugs, including the following:               
 
○ Aprepitant, artemether/lumefantine, aspirin, deferasirox, ibuprofen, ivacaftor, lomitapide, mifepristone, natalizumab, nimodipine, praziquantel, warfarin
 
 
 

Food and supplements that may interact with dexamethasone*

 
• Echinacea
 
• St. John's Wort
 
• Grapefruit, grapefruit juice, Seville oranges, star fruit
 

*\*Supplements may come in many forms, such as teas, drinks, juices, liquids, drops, capsules, pills, or dried herbs. All forms should be avoided.*

